9.4.1.2 Primary endpoint (objective response rate)

ORR (per RECIST 1.1 as assessed by the site Investigator) is defined as the number (%) of patients with a confirmed objective response of CR or PR and will be based on patients in the evaluable set.

A confirmed response of CR/PR means that a response of CR/PR is recorded at 1 visit and confirmed by repeat imaging not less than 4 weeks after the visit when the response was first observed with no evidence of progression between the initial and CR/PR confirmation visit. Therefore, data obtained up until progression, or the last evaluable assessment in the absence of progression, will be included in the assessment of ORR. Any patient who discontinues treatment without progression, receives a subsequent therapy, and then responds will not be included as responders in the ORR.

For sensitivity analysis, ORR may be assessed using the RECIST 1.1 site Investigator tumor data following a modification where any objective progression requires confirmation. Therefore, data obtained up until confirmed progression, or the last evaluable assessment in the absence of a confirmed progression, may be included in the assessment of ORR. Note that the response may be after an unconfirmed progression.

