For the immunotherapy arm only, a follow-up scan is requested following an overall timepoint assessment of progression by RECIST 1.1, preferably at the next scheduled imaging visit and no earlier than 4 weeks after the previous assessment of PD in the absence of clinically significant deterioration. Treatment will continue between the initial assessment of

progression and confirmation for progression. If a patient discontinues treatment (and/or receives a subsequent anticancer therapy) after the initial assessment of progression, then the patient should continue to be followed with scheduled imaging until confirmed objective disease progression.

It is important to follow the assessment schedule as closely as possible. Please refer to the study plan of the relevant arm appendix.

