9.4.1.3 Secondary endpoints

Secondary efficacy variables include DoR, DCR, TTR, PFS, and OS. Efficacy data will be summarized and analyzed based on the FAS.

Duration of response

DoR (per RECIST 1.1 as assessed by the site Investigator) will be defined as the time from the date of first documented response (which is subsequently confirmed) until the first date of documented progression or death in the absence of disease progression. The end of response should coincide with the date of progression or death from any cause used for the RECIST 1.1 PFS endpoint.

The time of the initial response will be defined as the latest of the dates contributing toward the first visit response of CR or PR. If a patient does not progress following a response, then their DoR will be censored at the PFS censoring time. DoR will not be defined for those patients who do not have documented response (which is subsequently confirmed).

Sensitivity analyses of DoR may be performed based on Investigator assessment according to RECIST 1.1 modified for confirmation of progression.

Disease control rate

DCR at 12 weeks is defined as the percentage of patients who have a best objective response of CR or PR in the first 13 weeks (to allow for a late assessment within the assessment window) or who have demonstrated SD for a minimum interval of 11 weeks (to allow for an early assessment within the assessment window) following the start of study treatment.

DCR will be determined programmatically based on RECIST 1.1 using site Investigator data and all data up until the first progression event.

Sensitivity analyses of DCR may be performed based on Investigator assessment according to RECIST 1.1 modified for confirmation of progression.

Time to response

TTR (per RECIST 1.1 as assessed by the Investigator) is defined as the time from the date of first dose until the first date of documented response (which is subsequently confirmed). The date of first documented response should coincide with that used for the RECIST 1.1 DoR endpoint. TTR will not be defined for those patients who do not have documented response (which is subsequently confirmed).

Progression-free survival

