9.5.2 Analysis of the primary variable(s)

For the primary endpoint, ORR will be estimated with 95% exact CIs separately for each treatment arm. The primary analysis will be based on the programmatically derived ORR based on RECIST 1.1 based on site Investigator assessments, and using all scans regardless of whether they were scheduled or not. A sensitivity analysis will be performed on programmatically derived ORR (RECIST 1.1 modified for confirmation of progression) to determine if there is any difference when using progression confirmation rules. The primary analysis population for ORR will be the FAS.

Summaries will be produced that present the number and percentage of patients with a tumor response (CR/PR). The number (%) of patients with a confirmed response and the number (%) of patients with a single visit response (ie, an unconfirmed response) will also be presented.

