8.2.1 Duration of treatment and criteria for treatment through progression

All treatment will be administered beginning on Day 1 until confirmed PD unless there is unacceptable toxicity, withdrawal of consent, or another discontinuation criterion is met. Treatment through progression will only be considered for arms containing durvalumab +/- tremelimumab.

Progression during treatment

During the treatment period patients may continue receiving therapy in the setting of unconfirmed radiologic progressive disease (PD) according to Response Evaluation Criteria in Solid Tumors version 1.1 (RECIST 1.1), at the Investigator's discretion, until progression is confirmed. A confirmatory scan is required following a RECIST 1.1 overall time point assessment of progression (PD), preferably at the next scheduled visit and no earlier than 4

weeks after the previous assessment of PD. Patients with PD by RECIST 1.1 (unconfirmed and confirmed) who, in the Investigator's opinion, continue to receive benefit from their assigned treatment and who meet the criteria for treatment in the setting of PD may continue to receive their assigned treatment for as long as they are gaining clinical benefit. However, patients will not be permitted to continue immunotherapy if progression occurs after confirmed response (CR or PR as defined by RECIST 1.1) to immunotherapy treatment in the target lesions (regardless of the appearance of new lesions) i.e the response and progression events both occurred in the target lesions while receiving immunotherapy during the same treatment period.

Patients with rapid tumour progression or with symptomatic progression that requires urgent medical intervention (eg, central nervous system metastasis, respiratory failure due to tumor compression, spinal cord compression) will not be eligible for continuing durvalumab ± tremelimumab.

Patients in the durvalumab + tremelimumab combination therapy arm meeting the retreatment criteria below will follow the same treatment guidelines followed during the original treatment period, including the same dose and frequency of treatments and the same schedule of assessments (with the exception of the PK, ADA, tumor biopsies, biomarker samples and optional PGx assessments, which do not need to be collected a second time).

Patients who meet the criteria for retreatment may only receive retreatment once.

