Patients receiving the durvalumab + tremelimumab combination therapy arm may undergo retreatment as described below:

Patients who complete the 4 dosing cycles of the combination of durvalumab and tremelimumab portion of the regimen (with clinical benefit per Investigator judgment), but subsequently have evidence of PD during the durvalumab monotherapy portion of the combination regimen, with or without confirmation according to RECIST 1.1, may restart treatment with the combination.

For all patients who are treated through progression and for patients who are restarting durvalumab + tremelimumab the Investigator should ensure that:

- The patient does not have any significant, unacceptable, or irreversible toxicities that indicate continuing treatment will not further benefit the patient
- There is absence of clinical symptoms or signs indicating clinically significant disease progression accompanied by a decline in WHO/ECOG performance status to >1
- There is absence of rapid disease progression or threat to vital organs or critical anatomical sites (eg, central nervous system metastasis, respiratory failure due to tumor compression, or spinal cord compression) requiring urgent alternative medical intervention.

- The patient still fulfills the eligibility criteria for this study with the exception of inclusion criteria numbers 4 and 7, and exclusion criteria number 19.

During the retreatment period, patients in the durvalumab + tremelimumab combination therapy group will resume durvalumab dosing at 1500mg q4w with 75 mg of tremelimumab q4w for 4 doses/cycles each. Patients will then continue with durvalumab monotherapy at 1500mg q4w, beginning at Week 16, 4 weeks after the last dose of combination therapy until disease progression.

Patients who AstraZeneca and the Investigator determine may not continue treatment after PD will be followed up for survival. Patients who have discontinued treatment due to toxicity or symptomatic deterioration, or who have commenced subsequent anticancer therapy, will be followed up until confirmed disease progression and for survival.

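### Arm A: a response produced by a second combination course can count towards the initial course in the confirmation-of-progression sensitivity ORR

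*Protocol*

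**What the plan says.** **Retreatment.** Appendix A Section 8.2.1 covers Arm A patients who complete the four combination cycles with clinical benefit and then progress on durvalumab monotherapy. Such patients, "with or without confirmation according to RECIST 1.1, may restart treatment with the combination". They "will resume durvalumab dosing at 1500mg q4w with 75 mg of tremelimumab q4w for 4 doses/cycles each", and then return to monotherapy. The same section adds: "Patients who meet the criteria for retreatment may only receive retreatment once".

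**Sensitivity ORR.** Section 9.4.1.2 describes a version of ORR in which any objective progression must be confirmed. The data window runs to confirmed progression, or to the last evaluable assessment if there is none, and the section notes: "Note that the response may be after an unconfirmed progression". Section 9.4.1.2 says this analysis may be done. Section 9.5.2 says it will be, and gives the aim: "to determine if there is any difference when using progression confirmation rules".

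**Secondary endpoints.** Section 9.4.1.3 offers the same modification as an option: "Sensitivity analyses of DoR may be performed based on Investigator assessment according to RECIST 1.1 modified for confirmation of progression". It has parallel sentences for DCR and PFS, and none for TTR.

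**Exclusions.** Section 9.4.1.1 uses every RECIST assessment whatever happens to treatment. The only treatment-based exclusion from responders, in Section 9.4.1.2, is for patients who stop without progression, receive a subsequent therapy and then respond.

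**Post-progression scans.** Section 6.1 states: "For the immunotherapy arm only, a follow-up scan is requested following an overall timepoint assessment of progression by RECIST 1.1".

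**The concern.** Appendix A Section 6.1 and Appendix F Section 5 give the reason for confirming progression: to tell pseudoprogression from true progression. That works only if the confirming scan reflects the treatment under which the progression was seen. When the combination is restarted on an unconfirmed progression, the next scan is taken under re-induction. An improvement on that scan may be an effect of the second course, yet the analysis rule treats the progression as unconfirmed and carries on counting.

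The comparison in Section 9.5.2 is meant to show what the confirmation rule does to ORR. If retreatment responses enter one side of it, a gap between primary and sensitivity ORR can no longer be put down to the confirmation rule alone. The protocol would be reporting a response to two courses as a late response to one.

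**Working it through.** The protocol states no figure for this point (its ORR and confidence-interval table is redacted), so there is nothing to reproduce. The check has three parts: the calendar, the confirmation rule, and the weight of one patient.

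**1. Calendar**
- Scans at weeks 8 and 12, then every 8 weeks (Appendix A Table 2, footnote m): 8, 12, 20, 28, 36, 44, 52.
- Monotherapy starts at week 16 (Appendix A Section 2.8).
- Retreatment doses every 4 weeks (Appendix A Section 8.2.1).

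Taking the restart in the week of the progression scan:

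| Progression and restart | Next scheduled scan | Second-course doses before it |
|---|---|---|
| Week 20 | Week 28 | Weeks 20, 24 |
| Week 28 | Week 36 | Weeks 28, 32 |
| Week 36 | Week 44 | Weeks 36, 40 |
| Week 44 | Week 52 | Weeks 44, 48 |

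Two second-course doses can precede the confirming scan each time. A later restart within the interval would leave fewer.

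**2. When progression becomes unconfirmed** (Appendix A Section 6.1; Appendix F Section 5)
- *Target lesions.* With nadir sum S, progression is confirmed if the sum is still at least 20% and at least 5 mm above nadir at the second consecutive visit, that is, at or above the larger of 1.2 × S and S + 5 mm. A tumour that merely holds its progressed size is confirmed. It must shrink back below that line to be unconfirmed.
- *Non-target or new lesions.* Confirmation needs significant worsening against the immediately preceding scan, or additional new lesions. If that disease stops worsening and no other criterion is met, the progression is unconfirmed.

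In either unconfirmed case the window in Section 9.4.1.2 stays open, and a later confirmed CR or PR makes the patient a responder. The exclusion for subsequent therapy does not apply, because retreatment is study drug given after progression. If progression was confirmed before the restart, the window has already closed and there is no problem.

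**3. Who can contribute**
- Appendix A Section 8.2.1 bars further immunotherapy when progression follows a confirmed response and both are in target lesions. Patients with stable disease are not barred, and they are the ones whose responder status could change.
- A response first seen at week 28 needs at least 4 more weeks to confirm: 28 + 4 = week 32 or later. The ORR cut-off is about 12 weeks after the last patient starts (Section 9.5.1), so the latest enrollees cannot contribute. Early enrollees can, as can the 21 patients treated in stages 1 and 2 (Appendix A Section 2.5.1) at the 40-patient analysis.

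**4. Weight of one reclassified patient**

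1/20 = 5.0 points; 1/21 = 4.8 points; 1/40 = 2.5 points.

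Illustrations with exact (Clopper-Pearson) 95% intervals; the responder counts are assumed:

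| n | With the retreatment response | Without it |
|---|---|---|
| 20 | 3/20 = 15.0% (3.2 to 37.9) | 2/20 = 10.0% (1.2 to 31.7) |
| 40 | 5/40 = 12.5% (4.2 to 26.8) | 4/40 = 10.0% (2.8 to 23.7) |

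**5. Reach across endpoints**
- Primary ORR, DoR and PFS use the first RECIST 1.1 progression, so they do not change.
- The 12-week DCR window closes at week 13, before a restart that follows progression on monotherapy planned from week 16.
- Modified PFS can be deferred: after an unconfirmed progression the event becomes the next confirmed progression or death.

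**The case against.** The strongest reply is that this concerns a sensitivity analysis in a descriptive study (Section 9.1), that no stated decision rule depends on it, and that a data-cut rule for a small subgroup is ordinary SAP detail. Much of that stands, and it limits how serious the point is. But the protocol does not leave the matter open. It sets the window at confirmed progression, accepts responses after unconfirmed progression, and already legislates for subsequent therapy. Programming Section 9.4.1.2 as written produces the problem.

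A second reply is that retreatment is protocol treatment within Arm A, so counting its effect is a legitimate policy. It could be, for an analysis labelled as the effect of the whole strategy. It does not fit an analysis whose stated aim is to isolate the confirmation rule.

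A third is that few patients will qualify: they need four completed cycles with benefit, no rapid progression and renewed eligibility, in a population whose median OS is put below 6 months (Appendix A Section 2.7.3). That is fair, and the number is unknown.

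Stronger readings that the documents do not support:
- *Any stabilisation on retreatment cancels the progression.* Not for target lesions, as the threshold above shows.
- *PFS events are lost.* They are deferred, and lost only if the patient is later censored.
- *DoR is lengthened.* The bar after a confirmed target-lesion response removes many of the patients whose DoR could be stretched, and new responders add durations of unknown length. The direction is uncertain.
- *TTR is distorted.* No modified TTR is planned.
- *The protocol calls these patients pseudoprogressors.* It does not say so of retreated patients; that follows only from the stated purpose of the confirmation rule.
- *Arms B and C have no post-progression scans.* Section 6.1 requests them for the immunotherapy arm only, and Appendix B Section 6.3 and Appendix C Section 7.3 image to objective progression, but Appendix F Section 4.1 asks for a follow-up scan in all patients. This is a conflict within the protocol, separate from retreatment.

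**Conclusion.** The point holds for the Arm A sensitivity ORR and, as a deferral of events, for the optional modified PFS. Two stated rules collide: restart is allowed on unconfirmed progression, and the modified analysis keeps counting until progression is confirmed. A retreatment response can therefore be credited to the initial course and raise the sensitivity ORR by 5.0 points per patient at n=20, or 2.5 at n=40. The total cannot be sized, because the protocol gives no number of retreated patients.

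This rests on three assumptions: the restart comes before the confirming scan, the second course shrinks or arrests disease enough to leave the progression unconfirmed, and no overriding rule stands in the SAP, which was not available here. A reader might infer that the trial's main efficacy results are biased. They are not: primary ORR, DoR and PFS are untouched, as in practice is 12-week DCR.

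**What to change.** Add one rule to Sections 9.4.1.2, 9.4.1.3 and 9.5.2 for the Arm A analyses under modified RECIST:
- tumour data after the first retreatment dose are excluded;
- the progression that led to retreatment counts as progression on the date of its scan, whether or not it was later confirmed;
- responses to retreatment are listed separately.

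At the same time, align Sections 9.4.1.2 and 9.5.2 on whether the sensitivity ORR may or will be done.

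The cost is one derivation rule and one listing. Dosing is already recorded in the CRF (Section 8.5), so no new data are needed. The sensitivity ORR and PFS may come out slightly less favourable. The primary analysis and the retreatment rule do not change.

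Separately, the post-progression imaging statements in Section 6.1, Appendix B Section 6.3, Appendix C Section 7.3 and Appendix F Section 4.1 must be reconciled before a modified analysis is run in Arms B and C.

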9.4.1.3 Secondary endpoints

Secondary efficacy variables include DoR, DCR, TTR, PFS, and OS. Efficacy data will be summarized and analyzed based on the FAS.

Duration of response

DoR (per RECIST 1.1 as assessed by the site Investigator) will be defined as the time from the date of first documented response (which is subsequently confirmed) until the first date of documented progression or death in the absence of disease progression. The end of response should coincide with the date of progression or death from any cause used for the RECIST 1.1 PFS endpoint.

The time of the initial response will be defined as the latest of the dates contributing toward the first visit response of CR or PR. If a patient does not progress following a response, then their DoR will be censored at the PFS censoring time. DoR will not be defined for those patients who do not have documented response (which is subsequently confirmed).

Sensitivity analyses of DoR may be performed based on Investigator assessment according to RECIST 1.1 modified for confirmation of progression.

Disease control rate

DCR at 12 weeks is defined as the percentage of patients who have a best objective response of CR or PR in the first 13 weeks (to allow for a late assessment within the assessment window) or who have demonstrated SD for a minimum interval of 11 weeks (to allow for an early assessment within the assessment window) following the start of study treatment.

DCR will be determined programmatically based on RECIST 1.1 using site Investigator data and all data up until the first progression event.

Sensitivity analyses of DCR may be performed based on Investigator assessment according to RECIST 1.1 modified for confirmation of progression.

Time to response

TTR (per RECIST 1.1 as assessed by the Investigator) is defined as the time from the date of first dose until the first date of documented response (which is subsequently confirmed). The date of first documented response should coincide with that used for the RECIST 1.1 DoR endpoint. TTR will not be defined for those patients who do not have documented response (which is subsequently confirmed).

Progression-free survival

PFS (per RECIST 1.1 as assessed by the site Investigator) will be defined as the time from the date of first dose until the date of objective disease progression or death (by any cause in the absence of progression) regardless of whether the patient withdraws from therapy or receives another anticancer therapy prior to progression.

Patients who have not progressed or died at the time of analysis will be censored at the time of the latest date of assessment from their last evaluable RECIST 1.1 assessment. However, if the patient progresses or dies after 2 or more missed visits, the patient will be censored at the

time of the latest evaluable RECIST 1.1 assessment. If the patient has no evaluable visits or does not have baseline data, they will be censored at Day 1 unless they die within 2 visits of baseline.

The PFS time will always be derived based on scan/assessment dates not visit dates.

RECIST 1.1 assessments/scans contributing toward a particular visit may be performed on different dates. The following rules will be applied:

- Date of progression will be determined based on the earliest of the dates of the component that triggered the progression on the first set of scans that indicates progression.
- When censoring a patient for PFS, the patient will be censored at the latest of the dates contributing to a particular overall visit assessment.

Sensitivity analyses of PFS may be performed based on Investigator assessment according to RECIST 1.1 modified for confirmation of progression.

Overall survival

OS is defined as the time from the date of first dose until death due to any cause. Any patient not known to have died at the time of analysis will be censored based on the last recorded date on which the patient was known to be alive.

Note: Survival calls will be made in the week following the date of data cut-off for the analysis, and if patients are confirmed to be alive or if the death date is post the data cut-off date, these patients will be censored at the date of data cut-off. Death dates may be found by checking publicly available death registries.

